We will randomize 30 overweight and obese ($BMI \geq 25 \text{ kg/m}^2$), adults age ≥ 50 yrs knee OA into one of 2 groups: an intensive dietary restriction-plus-exercise (D+E) group or an attention control (nutrition and health) group. Our minimum weight-loss goal for the weight-loss group will be 5% of body weight. The exercise intervention will meet 3 days/wk at the clinical site. The intervention will be comprised of both aerobic and strength training exercises. The nutrition and health group will meet 2 times over a 3 month period and will also receive a combination of text messages, emails (via personal email or Facebook), phone calls, and mailings for the remaining months. Participants will be allowed to choose their preferred method.

Measures

Western Ontario McMasters Universities Osteoarthritis Index (WOMAC). We will measure self-reported physical function and pain using the WOMAC (scores will be pulled from the KOOS Questionnaire in which the WOMAC is embedded). The LK version asks participants to indicate on a scale from 0 (none) to 4 (extreme) the degree of difficulty experienced in the last week due to knee OA. Individual scores for the 17 items are totaled to generate a summary score that could range from 0-68, with higher scores indicating poorer function. The pain index assesses participants' pain on the same scale, ranging from 0 (none) to 4 (extreme). The pain subscale consists of 5 items and total scores can range from 0-20, with larger scores indicating greater dysfunction. This instrument has been validated and recommended by the Osteoarthritis Research Society as the health status measure of choice in older adults with knee OA. In order to measure the minimal clinically improvement difference (MCID) participants will be asked to compare their knee pain to how it was at the beginning of the study.

Mobility. Our primary mobility measure will be 6-minute walk distance. Participants are told to walk as far as possible in 6 minutes on an established course. No personal timing devices are permitted, and participants are not provided feedback during the test. Results are significantly correlated to treadmill time and symptom-limited maximal oxygen consumption ($r = 0.52$ and $r = 0.53$, respectively) and have a 3-month test-retest reliability of 0.86 (Pennix et al). The Short Physical Performance Battery (SPPB) will also be used to measure mobility (Guralnik et al).

Submission Date: 9.9.22

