The SPPB is comprised of the following tests (balance, walking speed, and chair rise). A test of ascending and descending stair activity measured by the time (in seconds) it takes to ascend and descend a flight of 8 steps with 20cm (8 inch) step height and handrail will also be performed.

Cost Effectiveness Resource utilization will be collected by questionnaire, with domains including visits to clinicians (physicians, nurses, physical therapists, others), tests, medications, injections, surgery, alternative therapies. The Work Productivity and Activity Impairment index (WPAI) will be used to assess absenteeism and reduced productivity while at work (presenteeism).

Body weight, height, hip/waist circumference, BMI. Body weight and height will be obtained using standard techniques. Only persons with a $BMI \geq 25 \text{ kg/m}^2$ will be eligible. Circumference measurements will be collected using standard techniques.

[figure not shown]
Medical History, Medications, and Blood Pressure. Participants will be given forms to assess medical history and presence of comorbidities. Participants will also be asked questions about their medical history during the phone screen so as to reduce participant burden by identifying potential exclusion criteria. Participants will be administered a medication questionnaire adapted from the ARIC study and widely used in field research and in our prior studies at each testing visit (ARIC).

It is designed to obtain information about all prescription and over-the-counter medicines and supplements used during the 2 weeks prior to the interview (home or clinic). The participants will be mailed the medication form to fill out at home and will return the form to the interviewer. Participants may also be asked to provide the interviewer with all medicine containers so that the interviewer can transcribe the information. In addition participants will be encouraged to notify the study staff of any medication changes during the course of the study.

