In period 2 participants will focus on continued weight loss to reach the study weight loss goal of 5% of baseline weight. Participants will follow a weekly menu plan with recipes using traditional foods and the option to incorporate meal replacements. The traditional meals will contain 400-600 kcals, be low in fat and added sugars, and high in vegetables, fruits, and whole grains. Snacks may be a bar, fruit, or vegetable providing ~100-120 kcals. Daily caloric intake for each participant will be adjusted to his or her rate of weight change. Each group will be encouraged to take a daily multivitamin/mineral supplement containing no more than 100% of the Dietary Reference Intake for any particular nutrient.

Month 3

Period 3 will emphasize weight management over time. Participants will continue to follow a weekly menu plan with recipes using traditional foods and the option to incorporate meal replacements.

The exercise intervention will cover a 3-month period. The exercise program will consist of a 15-minute aerobic phase, a 20-minute strength-training phase, a second 15-minute aerobic phase, and a 10-minute cool-down phase. These sixty-minute exercise sessions will be conducted three days per week. Each participant will be prescribed an individual walking prescription by the exercise leader, which will be adjusted accordingly, as each

participant progresses throughout the 3 months. The exercise will be of moderate intensity. Alternate forms of aerobic exercise, such as but not limited to stationary bike, elliptical trainer, or treadmill walking, can be used in place of over-ground walking. This choice could be based on participant preference, the limitations of the exercise facility, or the participant's pain level.

Intervention Locations: The diet and exercise classes will be held at the Ginger Welch Complex.

All intervention staff in the WE-CAN study will be CPR certified. The exercise coordinator, who is part of the coordinating center and is responsible for maintaining exercise protocol congruity, will train and supervise the intervention staff. Intervention staff will meet monthly with the exercise coordinator to discuss any potential problems, risks, and concerns that have risen. AEDs will be available at each location. Emergency drills will be performed monthly in addition the AED will be checked monthly.

Nutrition & Health Intervention

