The nutrition and health (attention control) intervention will cover a 3-month period. There will be two total face to face group meetings over the 3 months, with one meeting each at months 1 and 3; and during the other month (month 2) participants will receive a combination of text messages, emails, and phone calls. Participants will be able to select their preferred method. Each group meeting will last approximately one hour and will be held at the Ginger Welch Complex in Cherokee, NC. The sessions will be interactive and will provide useful information on nutrition and general health topics. The Community Advisory Board will give input on the class sessions.

Procedures-Screening and Follow-up Visits.

Measurements	PSV	SV1	RV	FU3	Explanation
Informed Consent		x			
Questionnaires					
Eligibility Questionnaire	x				To determine eligibility
Medical History/Med History FU	xc	x		x	For eligibility and to document changes in health
Risk Stratification	xc	x			Used to screen cardiovascular risk
Comorbidities Questionnaire		x		x	
Randomization		x			
WOMAC		x		x	Pain is primary and function secondary outcomes. Will be taken from the KOOS
Knee Injury and Osteoarthritis Outcome Score (KOOS)		x		x	Assesses patient's opinion about their knee and associated problems
PASE scale		x		x	Physical Activity Scale for the Elderly
MOCA		x		x	Montreal Cognitive Assessment
EuroQol Quality of Life(EQ5D)		x		x	Quality of life measure
Resource Utilization		x		x	Visits to clinicians, tests, medications, injections, surgery, alternative therapies
Work Productivity and Activity Impairment Index		x		x	assesses absenteeism and presenteeism
DHQ II		x		x	NIH Diet History Questionnaire
SF-36		x		x	Health related quality of life (physical, mental)
Health Literacy		x		x	
Adherence Self Efficacy		x		x	Confidence in exercising at various intensities and frequencies
Adherence for Duration		x		x	Confidence in walking for different durations
Gait Efficacy		x		x	Confidence in completing tasks
Demographics		x			
Medication form		x		x	Atherosclerosis Risk in Communities form
Weight Efficacy Questionnaire		x		x	Self-Efficacy for Weight Management
PANAS		x		x	Positive and Negative Affect Scale
SWL		x		x	Satisfaction with Life
Perceived Stress		x		x	Stress
Pain Catastrophizing Scale		x		x	Catastrophizing
Intermittent and Constant Osteoarthritis Pain (ICOAP)		x		x	Intermittent and Constant Pain
CES-D		x		x	Depression
Transition Questionnaire				x	Knee pain

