Adverse Events				x	Also collected as they occur
Physical Performance Tests/Knee Exam					
height	xc	x			To determine BMI
weight	xc	x		x	To determine BMI
Knee exam		x			To determine eligibility
6 minute walk		x		x	Measure of mobility
Expanded Short Physical Performance Battery (SPPB)		x		x	Gait speed, sit to stand, balance tests; predicts disability
Randomization		x	x	x	mobility measures

Procedures-Screening and Follow-up Visits.

Prescreening visit (PSV). Individuals who contact our recruitment office in response to advertising will be asked a series of brief questions that focus on major eligibility criteria. A screening visit appointment will be made for participants who meet major eligibility criteria. A medical history form and a medication form will be mailed to the participants for them to complete.

Screening Visit One (SV1) SV1 includes an explanation of the study and obtaining informed consent. Other assessments include medical history and medication use (previously mailed), cardiovascular risk, height and weight (to calculate BMI), hip/waist circumference

Submission Date: 9.9.22

measurements, blood pressure, and a knee exam. The MOCA & CES-D will be administered. The following questionnaires will be given: demographics, cost effectiveness questionnaires, WOMAC, KOOS, Physical Activity Scale for the Elderly (PASE), Health-Related Quality of Life (HRQL), dietary intake questionnaires, health literacy, perceived stress, pain catastrophizing, and efficacy measures. Physical performance measures include the SPPB, 6 minute walk, GaitRite, and stair climb. This screening visit will last approximately 3 - 4 hours.

Randomization Visit (RV) At the RV an orientation to the group will be done.

3-month Follow-up Data Collection Visit (FU3): Participants will return to repeat all measures collected at baseline (minus the knee exam and demographics). The testing session will last approximately 2.5 – 3.5 hours. At the end of 3 months the participants will have a mini session on what the other group received.

Safety Monitoring Plan

An internal safety committee has been established to monitor participant safety and to evaluate the progress of the study.

Statistical Considerations

Data Management

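### Adverse events have one scheduled collection, at FU3; capture before then relies on contact that differs greatly between the arms, and a common monthly question would make it earlier and more even.

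*Protocol*

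**What the plan says.** **Scheduled collection.** In the table under Procedures-Screening and Follow-up Visits, the Adverse Events row has one mark, in the FU3 column, with the note "Also collected as they occur". The row does not distinguish the arms.

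**Other FU3 items, common to both arms.** Medical history is repeated ("For eligibility and to document changes in health"), as are the medication form and resource utilization ("Visits to clinicians, tests, medications, injections, surgery, alternative therapies").

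**Between visits.** The one participant prompt described is in Medical History, Medications, and Blood Pressure: "In addition participants will be encouraged to notify the study staff of any medication changes during the course of the study". It concerns medication, not adverse events.

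**Contact in the diet and exercise arm.** Exercise runs for 3 months on site: "These sixty-minute exercise sessions will be conducted three days per week". Under Month 1 the protocol adds two individual and two group diet sessions per month; it gives no count for months 2 and 3. Intervention staff meet the exercise coordinator monthly to go over problems, risks and concerns.

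**Contact in the control arm.** Nutrition & Health Intervention states: "There will be two total face to face group meetings over the 3 months", one in month 1 and one in month 3, and "during the other month (month 2) participants will receive a combination of text messages, emails, and phone calls". Study Design describes the remote part as also including "phone calls, and mailings for the remaining months". Neither place gives the number of remote contacts or says that they ask about adverse events.

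**Oversight.** The Safety Monitoring Plan names an internal safety committee and describes no procedure for finding events.

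**The concern.** Collecting events as they occur works only if the participant has an occasion to mention the event or staff have an occasion to notice it. Here one arm has such an occasion every two or three days and the other has two meetings in three months. The same event could reach staff, and through them the safety committee, within days in one arm and after weeks in the other. A minor event in the control arm could be forgotten before FU3, and one in a participant who misses FU3 might not be recorded at all.

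Timely and even safety monitoring is mainly at stake. Secondarily, if events are tabulated by arm, part of any excess in the diet and exercise arm could reflect closer observation. An analysis plan would not normally settle this, because it concerns how the data are collected.

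**Working it through.** The protocol states no figure for adverse-event detection, so there is none to reproduce. The check compares contact and waiting times.

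**Inputs from the protocol.** Three exercise sessions a week for 3 months; four diet sessions a month (stated under Month 1); two control meetings, in months 1 and 3; one scheduled adverse-event collection, at FU3; 30 participants.

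**Assumptions.** Three months is 12 or 13 weeks, so FU3 falls at day D = 84 or 91. Attendance is full. Event times are uniform over the period. No spontaneous or remote report comes first.

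**1. In-person sessions**
- Exercise: 3 × 12 = 36 to 3 × 13 = 39.
- With month 1 diet sessions only, counted separately: 36 + 4 = 40 to 39 + 4 = 43.
- With four diet sessions in each of 3 months: 36 + 12 = 48 to 39 + 12 = 51.
- Control: 2 meetings, plus an unknown number of remote contacts.

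The firm range is 36 to 39. The range 40 to 51 depends on how often diet sessions run after month 1. If diet sessions fall on exercise days, the number of distinct days stays at 36 to 39.

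**2. Mean wait from an event to the next in-person contact**

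Mean wait = (sum of squared gaps) / (2 × period).

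- Diet and exercise arm, weekly gaps of 2, 2 and 3 days: (4 + 4 + 9)/14 = 1.2 days. With gaps of 1, 1 and 5 days: (1 + 1 + 25)/14 = 1.9 days.
- Control arm, mid-month meetings at D/6 and 5D/6, then FU3. The gaps are D/6, 4D/6 and D/6, so the mean is D/4: 21.0 days (D = 84) or 22.8 days (D = 91).

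**3. Mean wait to a solicited adverse-event question**
- As written, FU3 only: D/2 = 42.0 or 45.5 days, the same in both arms.
- With questions mid-month in months 1, 2 and 3, then FU3. The gaps are D/6, D/3, D/3 and D/6, so the mean is 5D/36: 11.7 or 12.6 days in both arms.
- With the least favourable timing within months, for example days 0, 2D/3 and D: (4/9 + 1/9)D²/(2D) = 5D/18 = 23.3 or 25.3 days.

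**4. What the question does to the difference between arms**

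On the mid-month assumption, the control arm's mean wait to the next meeting, question or FU3 falls from 21 to 23 days to about 12 to 13. The other arm stays at 1 to 2 days through its sessions.

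**The case against.** The strongest reply is that the protocol contains no error here. It applies one rule to both arms, and unequal contact is inherent in comparing supervised exercise with two group meetings. Closer observation of the exercising arm is reasonable. The stated aims are feasibility and then pain, function, quality of life and walking distance; no between-arm comparison of adverse events is named. All of that stands, and it is why the point is a cheap improvement and not a fault.

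Other parts also stand:
- The interim routes listed are those the protocol describes. Consent material, which might tell participants how to report problems, is not in the text at hand, so it cannot be said that interim collection is purely passive.
- The monthly staff meeting might also serve the control programme, which the protocol likewise calls an intervention. The text does not make this clear.
- The 21 to 23 days set aside spontaneous and remote reports, and participants with an event may be the ones who miss exercise sessions. Contact is not detection.
- The committee's meeting schedule is not stated, so the delay in notice to it cannot be calculated.

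Two stronger readings are tempting. A reader might infer that counts by arm will be biased. The documents do not support that: FU3 asks both arms the same adverse-event, medical-history, medication and resource-use questions, so undercounting is confined to events forgotten by FU3 or to participants who miss it. A reader might also put the control wait at 42 to 46 days. That needs the first meeting on day 0 and the second on the day of FU3, which amounts to no interim meeting.

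The reply does not remove the difference in opportunity before FU3.

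**Conclusion.** The point holds in a limited form. With one scheduled collection and reliance on events surfacing by themselves, events before FU3 can come to notice later in the control arm, and minor or forgotten ones less often. The contrast in contact is firm: at least 36 on-site sessions with full attendance, against two meetings and an unstated number of remote contacts. The waiting times only illustrate it and rest on the assumptions listed above. The effect on recorded events cannot be computed from the protocol.

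The improvement in the solicited interval, from 42 to 46 days down to 12 to 13, applies to a quantity already equal between the arms; it shows earlier notice, not removal of the imbalance. The priority is low.

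The two descriptions of the control arm's remote contacts differ only slightly. With meetings in months 1 and 3, the remaining time can simply mean month 2; the plural and the mailings are what differ. This is a drafting point.

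**What to change.** 1. Ask both arms the same short structured adverse-event question in months 1, 2 and 3, before FU3. In months 1 and 3 use the control meeting and one existing session in the other arm. In month 2 use the same remote or self-completed mode in both arms. Mid-month timing keeps the intervals even.
2. Record for each event whether it was solicited or spontaneous, so that any table by arm can be based on solicited events.
3. As a minor matter, align Study Design and Nutrition & Health Intervention on the mode and months of the control arm's remote contacts.

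Neither intervention changes and no visit is added.

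**Cost.** 30 participants × 3 = 90 forms. The times per form and the month 2 non-response rate are assumptions.
- Asking, 2 to 5 minutes each: 3.0 to 7.5 hours.
- Entry from hard copy, 2 to 3 minutes each: 3.0 to 4.5 hours.
- Chasing 10 to 30% month 2 non-response (3 to 9 people) at 5 to 10 minutes each: 0.25 to 1.5 hours.
- Total: 6.25 to 13.5 staff hours.

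A minor amendment, preparation of the form, brief staff training and review of the added reports come on top and are not costed here. Some month 2 non-response will remain, and participants already seen three times a week complete extra short forms.
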